- For women of childbearing potential: agreement to remain abstinent (refrain from heterosexual intercourse) or use contraceptive methods that result in a failure rate of < 1% per year during the study treatment period and for a minimum of 60 days after the last dose of study drug or longer as required by local requirements for other standard of care medications. Women using estrogen-containing hormonal contraceptives as a method of contraception must also use a barrier.
  - A woman is considered to be of childbearing potential if she is postmenarcheal, has not reached a postmenopausal state (> 12 continuous months of amenorrhea with no identified cause other than menopause), and has not undergone surgical sterilization (removal of ovaries and/or uterus).
  - Examples of contraceptive methods with a failure rate of < 1% per year include bilateral tubal ligation, male sterilization, hormone-releasing intrauterine devices, and copper intrauterine devices. Established proper use of hormonal contraceptives that inhibit ovulation also have a failure rate of < 1% per year; however, women using estrogen-containing hormonal contraceptives as a method of contraception must also use a barrier, such as a male condom, in conjunction with the hormonal contraceptives.
  - The reliability of sexual abstinence should be evaluated in relation to the duration of the clinical trial and the preferred and usual lifestyle of the patient. Periodic abstinence (e.g., calendar, ovulation, symptothermal, or post-ovulation methods) and withdrawal are not acceptable methods of contraception.
- For men: agreement to remain abstinent (refrain from heterosexual intercourse) or use contraceptive measures, and agreement to refrain from donating sperm as defined below:
  - Men with female partners of childbearing potential must remain abstinent or use a condom plus an additional contraceptive method that together result in a failure rate of < 1% per year during the treatment period and for at least 120 days (16 weeks) after the last dose of study treatment. Men must refrain from donating sperm during this same period.
  - Men with pregnant female partners must remain abstinent or use a condom during the treatment period and for at least 28 days after the last dose of study treatment to avoid exposing the embryo.

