- For women of childbearing potential: agreement to remain abstinent (refrain from heterosexual intercourse) or use contraceptive methods listed in [Appendix 8](#) that result in a failure rate of  $< 1\%$  per year during the study treatment period and for a minimum of 60 days after the last dose of study drug or longer as required by local requirements for other standard of care medications. Women using estrogen-containing hormonal contraceptives as a method of contraception must also use a barrier.
  - A woman is considered to be of childbearing potential if she is postmenarcheal, has not reached a postmenopausal state ( $> 12$  continuous months of amenorrhea with no identified cause other than menopause), and has not undergone surgical sterilization (removal of ovaries and/or uterus).
  - Examples of contraceptive methods with a failure rate of  $< 1\%$  per year include bilateral tubal ligation, male sterilization, hormone-releasing intrauterine

devices, and copper intrauterine devices. Established proper use of hormonal contraceptives that inhibit ovulation also have a failure rate of < 1% per year; however, women using estrogen-containing hormonal contraceptives as a method of contraception must also use a barrier, such as a male condom, in conjunction with the hormonal contraceptives.

- The reliability of sexual abstinence should be evaluated in relation to the duration of the clinical trial and the preferred and usual lifestyle of the patient. Periodic abstinence (e.g., calendar, ovulation, symptothermal, or post-ovulation methods) and withdrawal are not acceptable methods of contraception.
- For men: agreement to remain abstinent (refrain from heterosexual intercourse) or use contraceptive measures, and agreement to refrain from donating sperm as defined below. Please also see [Appendix 8](#) for details:
  - Men with female partners of childbearing potential must remain abstinent or use a condom plus an additional contraceptive method that together result in a failure rate of < 1% per year during the treatment period and for at least 120 days (16 weeks) after the last dose of study treatment. Men must refrain from donating sperm during this same period.
  - Men with pregnant female partners must remain abstinent or use a condom during the treatment period and for at least 28 days after the last dose of study treatment to avoid exposing the embryo.

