## **4.6 PATIENT, TREATMENT, STUDY, AND SITE DISCONTINUATION**

### **4.6.1 Patient Discontinuation**

Patients have the right to voluntarily withdraw from the study at any time for any reason. Reasons for withdrawal from the study may include, but are not limited to, the following:

- Patient withdrawal of consent at any time
- Any medical condition that the investigator or Sponsor determines may jeopardize the patient's safety if he or she continues in the study
- Investigator or Sponsor determines it is in the best interest of the patient
- Patient non-compliance, as per Principal Investigator's discretion

Every effort should be made to obtain information on patients who withdraw from the study. The primary reason for withdrawal from the study should be documented on the appropriate eCRF. However, patients will not be followed for any reason after consent has been withdrawn. Patients who withdraw from the study will not be replaced.

If possible, the investigator will clarify the following:

- If the patient withdrew consent for the remaining study procedures *only* OR
- If the patient withdrew consent for the remaining study procedures as well as the use of all banked samples OR
- If the patient withdrew consent for the remaining study procedures as well as all use of study acquired clinical and laboratory data

If a patient discontinues the study prior to the Week 48 treatment completion visit, an early termination visit should be conducted. These patients should return for the 8-week safety follow-up visit in this study (see [Appendix 1](#)). If the patient is unable to return for a follow-up visit, the trial site may contact the patient by telephone to determine their clinical status.

Patients who discontinue the study during the safety follow-up period but prior to completion of the 8-week safety follow up will be asked to return to the clinic within 30 days ( $\pm 7$  days) after the last dose of study drug or last scheduled visit for an early termination visit.

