### **4.6.2 Study Treatment Discontinuation**

Patients must discontinue study treatment (and will continue in the study) if they experience any of the following:

- Requirement of any prohibited medication as defined in [Section 4.4.2](#)
- Treated with accepted immunosuppressive that exceeds the maximum dose as defined by the protocol (see [Section 4.4.1](#))
- Combination immunosuppressive medications not allowed in the inclusion and exclusion criteria (see [Section 4.1](#))

- Grade >2 AST or ALT elevation: (AST or ALT >3×ULN) in combination with total bilirubin >2×ULN or clinical jaundice as defined by Hy's law
- Grade ≥3 AST or ALT elevation: (AST or ALT >5×ULN)
- Grade 4 Neutropenia: ANC <500/mm^3
- Grade 4 Lymphopenia: absolute lymphocyte count (ALC) <200/mm^3
- Grade 4 Thrombocytopenia: platelet count <25,000/mm^3
- Pregnancy
- Malignancy (with the exception of non-serious local and resectable basal or squamous cell carcinoma of the skin)
- An episode of torsade de pointes

Patients must discontinue study treatment if they receive any new or increased dose of SLE treatment that is not specifically permitted in this protocol (see Section 4.4.1) and approved by the Medical Monitor.

Investigators may discontinue study treatment for:

- Any medical condition that may jeopardize the patient's safety if he or she continues on study treatment
- The best interest of the patient
- Patient non-compliance

If study treatment is discontinued prematurely, patients will be asked to stay in the study and continue with all scheduled visits for the remainder of the 48-week treatment period.

The primary reason for study treatment discontinuation should be documented on the appropriate eCRF. Patients who discontinue study treatment prematurely will not be replaced.

In some cases, study treatment may be resumed if approved by both the investigator and the Medical Monitor.

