## **5.4.3 Reporting Requirements for Pregnancies**

### **5.4.3.1 Pregnancies in Female Patients**

Female patients of childbearing potential will be instructed to immediately inform the investigator if they become pregnant during the study or within or within 8 weeks after the last dose of study drug, either in this study or an OLE, if initiated. A Clinical Trial Pregnancy Reporting Form should be completed and submitted to the Sponsor or its designee immediately (i.e., no more than 24 hours after learning of the pregnancy), either by faxing or by scanning and emailing the form using the fax number or email

address provided to investigators. Pregnancy should not be recorded on the Adverse Event eCRF. The investigator should discontinue study drug and counsel the patient, discussing the risks of the pregnancy and the possible effects on the fetus. Monitoring of the patient should continue until conclusion of the pregnancy. Any serious adverse events associated with the pregnancy (e.g., an event in the fetus, an event in the mother during or after the pregnancy, or a congenital anomaly/birth defect in the child) should be reported on the Adverse Event eCRF. In addition, the investigator will submit a Clinical Trial Pregnancy Reporting Form when updated information on the course and outcome of the pregnancy becomes available.

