c Week 48 visit is the last day of the study treatment period; however, no blinded study drug will be given at the Week 48 visit. The last dose of blinded study drug is the p.m. dose (evening) prior to the Week 48 visit. If eligible, patients may enroll into the open-label extension Study GA30066 to receive

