## Appendix 1 Schedule of Activities (cont.)

---

their first open-label dose of GDC-0853 on Day 1 of Study GA30066 (after a trough PK level is drawn) or they will proceed to the SFU period and return for the SFU visit on Week 56 (8 weeks after last dose of study drug). For patients enrolling into the OLE Study GA30066, Day 1 is the same day as the Week 48 visit of Study GA30044.

- d At an unscheduled visit (UV), adverse events and concomitant medications must be assessed. All other assessments are to be performed only if medically indicated based on the reason for the UV. If the patient returns for an unscheduled visit *or regular study visit* and has any evidence of increased SLE-activity requiring treatment, perform assessments required for a flare visit (FV).
- e A flare visit (FV) is any unscheduled visit where the patient *may* require escalation of treatment for increased SLE activity. *Assessments are to be performed only if medically indicated based on the reason for the FV.*
- f Patients will receive a telephone call from study staff to follow up for assessment of adverse events.
- g Either the ACR or SLICC diagnostic criteria for SLE may be used at screening to determine study inclusion.
- h Starting at the screening period, all patients must record their actual OCS use on a weekly basis and as instructed by study staff (see Section 4.3.2.4).
- i The OCS taper windows occur during Weeks 0-12 and Weeks 24-36 (tapering may be initiated after the Week 24 assessments are completed). For complete instructions on OCS tapering, see Section 3.3.6 and Appendix 4.

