## **Appendix 8**

### **Childbearing Potential, Pregnancy Testing, and Contraception**

#### **For Women**

All women of childbearing potential (including those who have had a tubal ligation) will have a serum pregnancy test at screening and a urine pregnancy test on study day 1 prior to administration of study drug and at subsequent clinic visits. If a urine pregnancy test result is positive, study drug will not be administered until pregnancy is ruled out. The result must be confirmed by a serum pregnancy test (conducted by the local laboratory).

Refer to Section 5.4.3 of the protocol for management of a patient with a confirmed pregnancy.

All female patients are considered to be of childbearing potential unless they meet one of the following criteria:

- The patient has been postmenopausal (non–therapy-induced amenorrhea) for at least 12 continuous months with no other identified cause
- The patient had a surgical bilateral oophorectomy (with or without hysterectomy) more than 6 weeks prior to enrollment
- The patient had a hysterectomy

Female patients of reproductive or childbearing potential who are unwilling to use a method of contraception that results in a failure rate of < 1 % per year or remain abstinent (refrain from heterosexual intercourse) during the treatment period and for at least 60 days after the last dose of study drug, or longer as required by local requirements for other standard of care medications, will be excluded from study participation.

Abstinence is acceptable only if it is in line with the preferred and usual lifestyle of the patient. Periodic abstinence (e.g., calendar, ovulation, symptothermal, or post-ovulation methods) and withdrawal are not acceptable methods of contraception.

Examples of contraceptive methods with a failure rate of < 1% per year include the following:

- Sterilization, bilateral surgical tubal ligation
- Intrauterine device
- Combined oral contraceptive pill\*
- Contraceptive transdermal patch (estrogen and progestin containing)\*
- Hormonal vaginal device
- Progestogen-only hormonal contraception associated with inhibition of ovulation
- Implants for contraception

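### Section 5.4.3.1 stops asking women to report pregnancies at 56 days after the last dose, while contraception is required to at least day 60; separately, the 16-week gloss on the men's 120 days is wrong

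*Combined protocol and SAP*

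**What the plan says.** **Reporting by women.** Section 5.4.3.1 requires immediate notice to the investigator from female patients of childbearing potential who "become pregnant during the study or within or within 8 weeks after the last dose of study drug, either in this study or an OLE". The doubled words are in the source.

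**Contraception for women.** The synopsis sets a "minimum of 60 days after the last dose of study drug or longer as required by local requirements for other standard of care medications". Section 4.1.1 requires it "for a minimum of 60 days after the last dose of study drug", with the same extension for local rules on other medicines. Appendix 8 excludes women unwilling to use contraception or abstain "for at least 60 days after the last dose of study drug, or longer as required by local requirements".

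**When a patient leaves.** Appendix 1, footnote c: "The last dose of blinded study drug is the p.m. dose (evening) prior to the Week 48 visit". Patients who do not enter the OLE "return for the SFU visit on Week 56 (8 weeks after last dose of study drug". The schedule puts Week 48 at Day 337 and Week 56 at Day 393, each with a window of 5 days either way. Section 4.6.1 foresees "Patients who discontinue the study during the safety follow-up period but prior to completion of the 8-week safety follow up". Under Section 4.6.2, if study drug is stopped early, "patients will be asked to stay in the study and continue with all scheduled visits for the remainder of the 48-week treatment period".

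**Men.** The synopsis and Section 4.1.1 require contraception for 120 days, glossed as 16 weeks. Appendix 8 gives 120 days, glossed as 4 months. Section 5.4.3.2 asks men to report partner pregnancies for 120 days, also glossed as 4 months.

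**The concern.** The sponsor has set 60 days as the shortest protected period for women because fetal malformations were seen in rats and rabbits (Section 1.3.1). One would expect the request to report pregnancies to run at least as long. For men it does: contraception and partner-pregnancy reporting both run 120 days. For women the reporting instruction is shorter, and no reason is given.

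Scheduled pregnancy testing ends with the follow-up visit. After that, the site mainly depends on the woman coming forward. At stake is a slightly incomplete record of pregnancies conceived inside the required contraception period, in a programme with little human pregnancy experience. No efficacy endpoint, error rate or power figure is involved.

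The gloss for men is a plain conversion error inside an eligibility criterion. A reader who worked in weeks would stop early.

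**Working it through.** **Women: the two periods**
- Reporting: 8 × 7 = 56 days after the last dose (5.4.3.1).
- Contraception: at least 60 days (synopsis, 4.1.1, Appendix 8).
- Difference: 60 − 56 = 4 days, namely days 57 to 60. These days are covered only if the woman is still in the study.

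**Women: when the study ends for a completer outside the OLE**
- Last dose on the nominal schedule: the evening before Day 337, so Day 336.
- Follow-up visit: Day 393, and 393 − 336 = 57 days after the last dose.
- Taking a visit exactly 8 weeks after the last dose, as footnote c describes it, the figure is 56 days.

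With v the day of the last visit counted from the last dose, the number of uncovered days is max(0, 60 − max(56, v)).

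| v (days) | Uncovered days |
|---|---|
| 56 or less | 4 |
| 57 (nominal schedule) | 3 |
| 58 | 2 |
| 59 | 1 |
| 60 or more | 0 |

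**Effect of the visit windows**
- Follow-up window alone: 388 − 336 = 52 to 398 − 336 = 62 days.
- Both windows: Week 48 can fall on Day 332 to 342, so the last dose falls on Day 331 to 341. Then v runs from 388 − 341 = 47 to 398 − 331 = 67 days.
- Appendix 2 also lets assessments move outside the window for holidays and the like, so 47 and 67 are not hard limits. The range of 0 to 4 uncovered days holds in every case.

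**Other women**
- Leaving during follow-up by day 56: 4 days.
- Stopping drug early and staying to Week 48: 0 days if the drug was stopped by Day 337 − 60 = 277. If such a woman also attends the Day 393 visit, 0 days if stopped by Day 393 − 60 = 333. The documents do not say plainly which applies.
- Entering the OLE: 0 days in this study, because dosing resumes on the day of the Week 48 visit and the reporting window then runs from the last OLE dose.

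**Men**
- Contraception against reporting: 120 − 120 = 0 days.
- The gloss: 16 × 7 = 112 days, which is 120 − 112 = 8 days short; 120 / 7 = 17.1 weeks.
- Four calendar months last from 28 + 31 + 30 + 31 = 120 to 31 + 31 + 30 + 31 = 123 days, so the 4-month gloss fits.

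**The case against.** **Such a pregnancy would still be reported.** A reader might infer that a pregnancy conceived in days 57 to 60 need not be reported at all. The documents do not support that. Section 5.4 lists pregnancies among the events that the investigator must report within 24 hours of learning of them, and sets no end date there. It points to Section 5.4.3 for details, but the 8-week limit there governs what the woman is told to disclose. It does not tell the investigator to hold back a later pregnancy. Anomalies and abortions (5.4.3.3) and later drug-related serious adverse events (5.6) also stay reportable. This objection stands and sets the size of the point: what is missing is the prompt to the woman.

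**Eight weeks is deliberate.** It matches the adverse event period (5.3.1), the serious event period (5.4.2.2) and the follow-up visit. That is a visible rationale. But the protocol does not hold pregnancy reporting to that period for men, where it runs to 120 days to match contraception.

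**The phrase about being in the study is undefined.** Section 3.2.2 defines the end of study for the trial as a whole, and on that reading nearly all women are covered. Section 3.2.1, however, counts time on study per patient and stops at the 8-week follow-up, so a site could well read it that way.

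**The men's gloss changes nothing.** This also stands. A reader might infer that men may stop contraception at 16 weeks, or that partner pregnancies go unreported for 8 days. Neither follows: the figure of 120 days appears in all four places.

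**Conclusion.** The mismatch is real and minor. Women are asked to report for 56 days after the last dose and to use contraception for at least 60. For a woman who leaves the study before day 60 and does not enter the OLE, up to 4 days of required contraception carry no prompt to report a conception, and 3 days on the nominal schedule. This rests on two assumptions: that a patient's study ends at her own last visit, and that the 60-day minimum applies. Where local rules for other medicines require longer contraception, the two periods differ by more, but the documents give no figure and that extra time is not tied to GDC-0853. The consequence is limited to self-reporting.

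The 16-week gloss for men is an arithmetic slip of 8 days in two places, with no reporting gap behind it.

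**What to change.** 1. In Section 5.4.3.1, replace *within or within 8 weeks* with *within 60 days* and leave the rest of the sentence, including the OLE clause, as it is. This also removes the doubled words. Do not add an extension to the end of any longer local contraception period. That period depends on other medicines, and for a woman who stays on one it could have no fixed end.
2. In the synopsis and Section 4.1.1, change the gloss on the men's 120 days from *16 weeks* to *4 months*, matching Section 5.4.3.2 and Appendix 8.
3. Align the consent form if it carries the same figures.

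The cost is wording in three places, plus the consent form if needed, and it can wait for the next amendment. No visit or test is added. The downside is an occasional extra pregnancy to report and follow to outcome, and a pregnancy window 4 days longer than the adverse event window.

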#### **5.4.3.2 Pregnancies in Female Partners of Male Patients**

Male patients will be instructed through the Informed Consent Form to immediately inform the investigator if their partner becomes pregnant during the study or within 120 days (4 months) after the last dose of study drug. A Clinical Trial Pregnancy Reporting Form should be completed and submitted to the Sponsor or its designee immediately (i.e., no more than 24 hours after learning of the pregnancy), either by faxing or by scanning and emailing the form using the fax number or email address provided to investigators. Attempts should be made to collect and report details of the course and outcome of any pregnancy in the partner of a male patient exposed to study drug. *When permitted by the site, the pregnant partner would need to sign an Authorization for Use and Disclosure of Pregnancy Health Information to allow for follow-up on her pregnancy. If the authorization has been signed, the investigator should submit a Clinical Trial Pregnancy Reporting Form when updated information on the course and outcome of the pregnancy becomes available.* An investigator who is contacted by the male patient or his pregnant partner may provide information on the risks of the pregnancy and the possible effects on the fetus, to support an informed decision in cooperation with the treating physician and/or obstetrician.

